2.8.4 Other safety data

2.8.4.1 ECG and cardiac imaging data

ECG data will be collected at screening and all data, including unscheduled visits, will be listed.

2.8.4.2 Vital signs

All vital signs (systolic and diastolic blood pressure [mmHg], pulse rate [sitting/beats per minute], weight [kg], height [cm], BMI [kg/m²] and waist/hip circumference) will be descriptively summarized at each visit by treatment group and open-label sacubitril/valsartan. Change from baseline will also be presented.

A separate summary table will be presented with the number and percentages of patients having notable vital signs based on changes relative to baseline values (see Section 5.4 for a list of notable vital signs) by study phase (see Section 2.1.1 for study phase definitions).

The number and percentages of patients having symptomatic hypotension will also be summarized by study phase. The following variables associated with symptomatic hypotension will also be presented: symptoms occurring while standing, any treatment or medication change as a result of episode, lowest documented systolic blood pressure, systolic blood pressure position, lowest documented diastolic blood pressure and diastolic blood pressure position. A listing for symptomatic hypotension will also be presented.

2.8.4.3 Heart Failure Event

Any new heart failure event information will be collected and listed. The following will be presented:

• Type of event (HF hospitalization [hospital stay ≥24 hours], Heart failure emergency department visit, Urgent/unplanned heart failure office visit, Worsening heart failure

during the index hospitalization [qualifying heart failure event], None of the aforementioned types occurred with, or apply to, this HF event)

- Symptoms of worsening HF (Dyspnea [Dyspnea at rest, Dyspnea on exertion, Orthopnea, Paroxysmal nocturnal dyspnea, Tachypnea], Decreased exercise tolerance [reduced ability to perform activities that induce physical exertion due to dyspnea or fatigue], Fatigue [lack of energy, extreme tiredness, inability to complete usual activities], Worsening end-organ perfusion – [Confusion (thought to be from low cardiac output), Reduced urine output], Symptoms of volume overload – [Lower extremity swelling, Increased abdominal distension)], Other)
- Physical exam signs of worsening HF (Peripheral edema, Increased abdominal distension or ascites [in the absence of hepatic disease], Pulmonary rales/crackles, Elevated jugular venous pressure and/or hepatojugular reflux, New or worsening 3rd heart sound, Clinically significant weight gain thought to be related to fluid retention [>3 4 lbs. in 3 to 4 days], Other)
- Laboratory evidence of worsening HF (Increased NT-proBNP [>2,000 pg/mL], Radiographic evidence of pulmonary congestion, Right heart catheterization with pulmonary capillary wedge pressure ≥18 mmHg, central venous pressure ≥12 mmHg, or a cardiac index of <2.2 L/min/m², Other)
- Increased or additional therapy (No, Yes, Unknown)
 - Therapy type (Augmentation of oral diuretic therapy with additional diuretic, Initiation of intravenous diuretic, Uptitration of intravenous therapy, if already on therapy, Initiation of inotrope, or vasodilator therapy, Initiation of percutaneous mechanical circulatory support, Initiation of temporary surgical support [ECMO or temporary surgical ventricular assist device (VAD) i.e. centrimag], Implantation of durable LVAD, Listed for heart transplantation)
- Evidence of cardiogenic shock (No, Yes, Unknown)
- Blood sample collected for BNP or NT-proBNP (No, Yes, Unknown)
 - \circ BNP result (pg/mL)
 - \circ NT-proBNP result (mg/mL)
- Contributors/precipitants of worsening heart failure (Medication nonadherence, Dietary indiscretion, Acute coronary syndrome, Other systemic illness [Respiratory infection, Urinary tract infection, Other])

2.8.4.4 HF Signs and Symptoms

Heart failure signs and symptoms will be collected at screening, randomization and at post randomization visits. The number and percentage of the following parameters will be summarized at each visit by treatment group and open-label sacubitril/valsartan:

- Heart failure signs or symptoms within the past 24 hours prior to this visit (No, Yes)
- Rales (Not present, Basilar only, >1/3 of lung filled, Not done)

- Peripheral edema (Absent, Trace, Feet and ankles, Lower legs or thighs, Sacrum, Not done)
- Current NYHA heart failure classification (Class I, Class II, Class III, Class IV, Not done)
- Fatigue (Not present, Seldom, Frequent, Continuous, Not done)
- Dyspnea (Not present, Seldom, Frequent, Continuous, Not done)
- Orthopnea (Not present, Seldom, Frequent, Continuous, Not done)

2.8.4.5 Hospitalization

Information related to hospitalization will be listed. The following will be presented:

- Type of hospitalization (Elective, Planned, Unplanned)
- Reason for hospitalization (refer to eCRF for list of reasons)
- Patient discharged (No, Yes, Unknown)
 - Duration of hospitalization in days [*date of discharge date of admission* + 1]
- Patient admitted to ICU or Coronary Care Unit (CCU) (No, Yes, Unknown)
 - Number of days in ICU or CCU
- Discharge disposition (Home or with family/friends, Rehabilitation facility, Skilled nursing facility, Death, Unknown)

2.8.4.6 Angioedema

Data collected from the angioedema assessment and questionnaire at screening, randomization and follow-up visits will be summarized. Separate summaries will be produced for all angioedema and positively adjudicated angioedema. The number and percentage for categorical variables and summary statistics for continuous variables of the following will be presented by visit, treatment group and open-label sacubitril/valsartan:

- Outcome (Not recovered/Not resolved, Recovered/Resolved, Recovering/Resolving, Recovered/Resolved with Sequelae, Fatal, Unknown)
 - Duration of angioedema in days [*end date start date* + 1]
- Timing of event (After first dose, after multiple doses, dose not given) [not asked at screening]
 - Study medication discontinued due to event (No, Yes, Unknown)
 - Event occurred within 1 day of dosing (Within 1 day of dose but less than or equal to 1 hour, within 1 day of dose but greater than 1 hour, After 1 day of dosing, Unknown)
- History of prior angioedema or angioedema like event (No, Yes, Unknown)
 - If yes, medications taken at time of previous event:

- ACE inhibitor (No, Yes, Unknown)
- ARB (No, Yes, Unknown)
- Renin inhibitor (No, Yes, Unknown)
- Other medications (No, Yes, Unknown)
- Presence of hereditary angioedema (No, Yes, Unknown)
- Any family members with history of angioedema-like events (No, Yes, Unknown)
- Signs and symptoms for current event
 - Shortness of breath/dyspnea (No, Yes, Unknown)
 - Difficulty swallowing/dysphagia (No, Yes, Unknown)
 - Difficulty speaking/dysarthria (No, Yes, Unknown)
 - Pain on swallowing/odynophagia (No, Yes, Unknown)
 - Stridor (No, Yes, Unknown)
 - Abdominal pain (No, Yes, Unknown)
 - Other (No, Yes, Unknown)
- Edema present (No, Yes)
 - Periorbital edema (No, Yes, Unknown)
 - Head edema (No, Yes, Unknown)
 - Neck edema (No, Yes, Unknown)
 - o Lip edema (No, Yes, Unknown)
 - Tongue edema (No, Yes, Unknown)
 - o Throat edema (No, Yes, Unknown)
 - Submandibular edema (No, Yes, Unknown)
 - Genitalia edema (No, Yes, Unknown)
 - Extremities edema (No, Yes, Unknown)
 - Other (No, Yes, Unknown)
- Previous edematous episodes (No, Yes, Unknown)
 - Number of previous edematous episodes
- ACEi taken in the past (No, Yes, Unknown)
- ACEi taken during trial participation after screening (No, Yes, Unknown) [not asked at screening]
 - Dose changed within 2 days of event (No, Yes, Unknown)
- ARB taken in the past (No, Yes, Unknown)

- ARB taken during trial participation after screening (No, Yes, Unknown) [not asked at screening]
 - Dose changed within 2 days of event (No, Yes, Unknown)
- Patient suffering from influenza, common cold or upper respiratory tract infection (No, Yes, Unknown)
- Medication allergies (No, Yes, Unknown)
- Food allergies (No, Yes, Unknown)
- Potential causes of angioedema-like event
 - Food (No, Yes, Unknown)
 - Insect bite (No, Yes, Unknown)
 - Animal exposure (No, Yes, Unknown)
 - Medication (No, Yes, Unknown)
 - Dental work (No, Yes, Unknown)
 - Pollen (No, Yes, Unknown)
 - Dust (No, Yes, Unknown)
 - Concomitant disease (No, Yes, Unknown)
 - Idiopathic (No, Yes, Unknown)
 - Other (No, Yes, Unknown)
- Medical intervention (No, Yes)
 - Administration of H-1 blocker (No, Yes)
 - Administration of H-2 blocker (No, Yes)
 - Administration of steroids (No, Yes)
 - Administration of epinephrine (No, Yes)
 - Admission to hospital (No, Yes)
 - Admission to ER (No, Yes)
 - Endotracheal intubation (No, Yes)
 - Tracheostomy (No, Yes)
 - Discontinuation of ACE inhibitor (No, Yes)
 - Discontinuation of ARB (No, Yes)
 - o Other

All assessment data will be listed. The adjudicated assessment of the event will be listed separately.

In addition, key characteristics of positively adjudicated angioedema will be summarized with descriptive statistics by study phase as defined in Section 2.1.1.

2.9 Pharmacokinetic endpoints

Not applicable.

2.10 PD and PK/PD analyses

Not applicable.

2.12 Biomarkers

BNP and NT-proBNP will be collected and descriptively summarized by visit, treatment group and open-label sacubitril/valsartan. Values and the change from baseline for each parameter will be summarized by visit, treatment group and open-label sacubitril/valsartan. Analyses will be based on the FAS. BNP and NT-proBNP values will be based on clinical laboratory samples processed and assessed by the central laboratory.

Additional biomarker measurements believed to be relevant to the pathophysiology of the disease processes of heart failure and dysfunction will also be collected and summarized by visit, treatment group and total. These may include, but no limited to those assessing cardiac and renal benefit or biomarkers related to the study treatment mechanism of action such as:

- Neurohormones BNP and NT-proBNP
- hs-Troponin T

Additional analysis of biomarkers is discussed in Sections 2.5, 2.7 and 2.13.

Biomarker samples from patients who withdrew consent will not be analyzed by the central laboratory.

2.14 Interim analysis

No interim analysis is planned.

3 Sample size calculation

Assuming a significance level of 0.05 and 85% power, a sample size of 882 patients would be needed to detect an 18% reduction in the geometric mean of the time-averaged proportional change from baseline (average of Weeks 4 and 8) in NT-proBNP for the sacubitril/valsartan treatment group assuming a value of 0.95 for the enalapril group, a common standard deviation of 0.85 and a 25% rate of missing/non-evaluable samples. The estimates are based on the day 5 to day 14 data from the RELAX-AHF study. The standard deviation estimate is supported by data from PARADIGM.

The assumption of a 18% reduction in the geometric mean for NT-proBNP for the sacubitril/valsartan treatment group vs. the enalapril group is consistent with NT-proBNP results seen in PARADIGM (26% and 25% relative reduction of sacubitril/valsartan vs. enalapril at Week 4 and Month 8 respectively), PARAMOUNT (23% relative of sacubitril/valsartan vs. valsartan at Week 12) and RELAX-AHF (19% relative reduction of serelaxin vs. placebo at Day 2).

Sample size and power for various rate of reduction in sacubitril/valsartan group given alpha = 0.05 are given in Table 9-1 in the protocol.

4 Change to protocol specified analyses

The following changes to protocol specified analyses were made:

- Specified the following additional biomarkers as secondary endpoints:
 - UcGMP to urinary creatinine ratio
 - o BNP
 - NT-proBNP to BNP ratio

• Added sensitivity analyses for the following endpoints using the "strict" baseline definition (i.e., collection date:time < first dose date:time):

- Clarified that tables summarizing demographics and baseline data will be run only on the FAS, and not also on the RS as indicated in the protocol
- Replaced supportive analysis of the primary endpoint consisting of summary statistics and t-test p-values for comparing treatment groups on the proportional change from baseline in a logarithmic scale at Weeks 4 and 8 with ANCOVA at Weeks 4 and 8

• Added Weeks 4 and 8 to the analysis of change from baseline in biomarkers defined as secondary endpoints

patients from the PPS regardless of the study phase in which they occur

5 Appendix

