4.1 Inclusion criteria

Patients eligible for inclusion in this study have to fulfill all of the following criteria:

1. Possess the capacity to provide written informed consent which must be obtained before any assessment is performed.

Confidential

- 2. Patients \geq 18 years of age, male or female.
- 3. Currently hospitalized for ADHF. Patients with a diagnosis of acute heart failure had to have symptoms and signs of fluid overload (i.e. jugular venous distention, edema or rales on auscultation or pulmonary congestion on chest x-ray) at time of hospitalization.
- 4. Eligible patients will be randomized no earlier than 24 hours and up to ten days after presentation while still hospitalized as long as meet the following definition of stable status:
 - SBP ≥100mm Hg for the preceding 6 hours prior to randomization; no symptomatic hypotension
 - No increase (intensification) in i.v. diuretic dose within last 6 hours prior to randomization
 - No i.v. inotropic drugs for 24 hours prior to randomization
 - No i.v. vasodilators including nitrates within last 6 hours prior to randomization
- 5. LVEF ≤40% within the past 6 months (including current hospitalization) using echocardiography, multi gated acquisition scan (MUGA), CT scanning, MRI or ventricular angiography, provided no subsequent study documented an EF of>40%.
- 6. Elevated NT-proBNP \geq 1600pg/mL OR BNP \geq 400 pg/mL during current hospitalization.

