9.1 Analysis sets

The following patient sets will be used for the statistical reporting and analyses:

The Randomized Set will consist of all randomized patients.

The Full Analysis Set (FAS) will consist of all randomized patients with the exception for those patients who have not been qualified for randomization and have not received study drug, but have been inadvertently randomized into the study. Following the intent-to-treat principle, patients will be analyzed according to the treatment to which they were assigned at randomization. Efficacy variables will be analyzed based on the FAS as the primary set.

The Safety Set (SAF) will consist of all randomized patients who received at least one dose of study drug. Patients will be included in the analysis according to the treatment actually received. The Safety Set will be used for the analyses of safety variables.

The Per-Protocol (PP) set will be a subset of the FAS which will consist of the patients who do not have major deviations from the protocol procedures in the double-blind study stage. Major protocol deviations will be pre-specified prior to unblinding treatment codes for analyses. This supplemental efficacy set will be used to support the primary analysis results.

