2.2 Analysis sets

The following analysis data sets will be used in the analyses:

Randomized Set (RS): The RS will consist of all randomized patients.

Full Analysis Set (FAS): The FAS will consist of all randomized patients with the exception for those patients who have not been qualified for randomization and have not received study treatment, but have been inadvertently randomized into the study. Following the intent-to-treat principle, patients will be analyzed according to the treatment to which they were assigned at randomization. Efficacy variables will be analyzed based on the FAS as the primary set.

Safety Set (SS): The SS will consist of all randomized patients who have received at least one dose of study treatment. Patients will be included in the analysis according to the treatment actually received. The SS will be used for the analyses of safety variables.

Per-Protocol Set (PPS): The PPS will be a subset of the FAS, which will consist of the patients who do not have major deviations from the protocol procedures. Major protocol deviations will be pre-specified prior to unblinding treatment code for analysis. This supplemental analysis set will be used to support the primary analysis results.

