5.6 Rule of exclusion criteria of analysis sets

Table 1 Protocol deviations that cause subjects to be excluded **Deviation Description of Deviation Exclusion in Analyses** ID D01 Patient met one or more of the Exclusion from PPS Discontinuation of Study Drug criteria but study drug was not discontinued E02 Patient is enrolled in another clinical **Exclusion from PPS** trial involving an investigational agent or investigational device E03 Patients has а **Exclusion from PPS** history of hypersensitivity, known or suspected contraindications, or intolerance to the study drugs, including ACEIs, ARBs, or Sacubitril (NEP inhibitor) **Exclusion from PPS** E04 Patient has a history of angioedema related to previous ACE inhibitor or ARB therapy E11 The patient had implantation of a **Exclusion from PPS** cardiac resynchronization therapy device (CRTD) within the prior 3 months from Visit 1, the patient intends to have implantation of a cardiac resynchronization therapy device (CRTD) E19 Patient is a pregnant or nursing **Exclusion from PPS** (lactating) women, where pregnancy is defined as the state of a female after conception and until the termination of gestation, confirmed by a positive hCG laboratory test LVEF was not < 40% within the past Exclusion from PPS I07 6 months (including current hospitalization) using echocardiography, multi gated acquisition scan (MUGA), CT scanning 109 Patient did not have an elevated NT-**Exclusion from PPS** proBNP \geq 1600pg/mL or BNP \geq 400 pg/mL during current hospitalization

Deviation ID	Description of Deviation	Exclusion in Analyses
M01	Patient had concomitant intake of a prohibited medication as outlined in the protocol	Exclusion from PPS
O04	Patient randomized in error and not dosed with study drug	Exclusion from FAS and PPS
O05	Missing NT-ProBNP sample at either baseline, week 4 or week 8	Exclusion from PPS
O06	Patient took first dose of study drug before baseline NT-proBNP sample was drawn	Exclusion from PPS
007	Patient missed 1 or more consecutive dose(s) of study drug immediately or prior to visit 5 or visit 7	Exclusion from PPS

Table 2Patient Classification

Analysis Set	PD ID that cause subjects to be excluded	Non-PD criteria that cause subjects to be excluded
RS	NA	Not randomized
FAS	O04	Not in RS
PPS	D01, E02, E03, E04, E11, E19, I07, I09, M01, O04, O05, O06, O07	Not in FAS
SS	NA	No double-blind study treatment received

6 Reference

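### The SAP drops the protocol's double-blind limit on per-protocol exclusions, so deviations after Week 8 can remove patients whose endpoint data are already complete

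*SAP*

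**What the plan says.** Protocol 9.1 defines the per-protocol set as those members of the full analysis set (FAS) who "do not have major deviations from the protocol procedures in the double-blind study stage".

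SAP 2.2 restates the definition without the phase limit: "patients who do not have major deviations from the protocol procedures. Major protocol deviations will be pre-specified prior to unblinding treatment code for analysis".

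SAP Section 4 opens with "The following changes to protocol specified analyses were made", and the end of its list contains the fragment "patients from the PPS regardless of the study phase in which they occur". The start of that sentence is not in the public text. In the SAP document history, item 52 points to Sections 2.2 and 4, but its description is also missing.

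SAP 5.6 lists 13 codes that exclude a patient from the per-protocol set (PPS). M01 reads "Patient had concomitant intake of a prohibited medication as outlined in the protocol", with no date or phase. D01 (a discontinuation criterion was met but study drug continued) is equally open-ended.

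SAP 2.1.1 ends the double-blind phase on the date of the Week 8 visit, inclusive, and starts the open-label phase after it. The primary endpoint (SAP 2.5.1) uses Weeks 4 and 8 and is analysed in the FAS. SAP 2.5.4 repeats that analysis in the PPS as support.

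**The concern.** A per-protocol set is meant to show whether the result holds among patients whose treatment and measurements followed the plan up to the endpoint. A deviation that first occurs after the Week 8 sample cannot have altered either NT-proBNP value. Excluding on it removes valid data and makes membership of the set depend on what happened afterwards.

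This matters more here because the post-Week 8 period differs by randomized arm. All patients then move to open-label sacubitril/valsartan, so former enalapril patients change drug while the others continue on theirs. Open-label deviations could therefore be unequal between the arms and could be related to NT-proBNP. If so, the PPS could differ from the FAS for reasons unconnected with adherence in the double-blind period, and agreement or disagreement between the two would be harder to interpret.

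**Working it through.** **1. Which codes can first arise after Week 8**

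| Codes (SAP 5.6) | What they concern | Can first arise in open label? |
|---|---|---|
| D01 | Discontinuation criterion met, drug not stopped | Yes |
| M01 | Prohibited medication | Yes |
| E02 | Enrolment in another trial | Possibly |
| E03, E04, E11, E19, I07, I09 | Eligibility | No |
| O04 | Randomized in error and not dosed | No |
| O05, O06, O07 | Baseline, Week 4 or Week 8 sample; dosing before Visit 5 or 7 | No |

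So two codes, perhaps three, carry the problem. O05 and O07 show that the same table already ties some exclusions to the endpoint window.

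**2. The plan's own figure**

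Inputs from protocol 9.7 and SAP Section 3: ratio 0.82, log-scale SD 0.85, two-sided alpha 0.05, power 85%, 25% non-evaluable.

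- ln(0.82) = −0.1985.
- Per arm: 2 × 0.85² × (1.960 + 1.036)² / 0.1985² ≈ 330.
- 330 / 0.75 = 440 per arm, 880 in total.
- The exact t calculation gives 331 per arm, and 662 / 0.75 = 882.7.

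The stated 882 is reproduced. The point does not dispute it.

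**3. Possible shift in the PPS estimate (assumed inputs)**

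The documents do not say how many patients deviate after Week 8, or how their values differ. If a fraction f of an arm is removed and their mean log ratio lies δ above the arm mean, the mean of those left moves by −fδ/(1 − f). Assume δ = 0.5:

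- f = 0.08: −0.04/0.92 = −0.0435.
- f = 0.03: −0.015/0.97 = −0.0155.
- Difference: 0.0435 − 0.0155 = 0.028.

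| Assumed loss (enalapril / sacubitril/valsartan) | Log effect | Ratio |
|---|---|---|
| 8% / 3% | −0.198 + 0.028 = −0.170 | 0.84 |
| Equal | −0.198 | 0.82 |
| 3% / 8% | −0.198 − 0.028 = −0.226 | 0.80 |

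For scale, 882 × 0.75 = 661.5 evaluable patients give a standard error of 0.85 × √(4/661.5) = 0.066. A shift of 0.028 is therefore about 0.4 standard errors.

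**4. Possible loss of precision (assumed inputs)**

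Starting from 661.5 evaluable patients (power 85.1%), an extra PPS loss of 1% gives 84.8%, 5% gives 83.3% and 10% gives 81.3%. Precision is a minor issue.

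**The case against.** The strongest reply has four parts.

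- **The sentence in SAP Section 4 is incomplete.** Which deviations it covers cannot be read, and it may be only a subset. This stands as a limit on how firmly the rule can be stated. The point does not rest on that sentence alone, because SAP 2.2 drops the phase limit and SAP 5.6 dates neither D01 nor M01.
- **The change is declared.** It sits in a list of changes, in an amendment made before database lock, and the exclusion rules followed a final review of protocol deviations. A reader might infer a concealed contradiction between protocol and SAP. The documents do not support that. Declaring the change does not make it sound, however, and the available text gives no reason for it.
- **The PPS is only supportive, and it already conditions on post-randomization events** such as missed doses and missing samples. This is correct. Those events fall within the period that produces the endpoint, whereas open-label deviations do not.
- **A difference between arms is speculative.** All patients undergo the same washout and take the same open-label drug. This stands: an imbalance is plausible but not shown.

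A reader might also infer that code I07 removes eligible patients. As printed it reads "LVEF was not < 40% within the past" and names imaging methods only as far as CT scanning, while inclusion criterion 5 begins "LVEF ≤40% within the past 6 months (including current hospitalization) using" and goes on to include MRI and ventricular angiography. The documents do not support that inference. The sign may be a text-reading error and the list may be abbreviated or cut. The SAP's own objective (1.2) uses ≤40%, and its subgroup bands (2.2.1) place 40% below the >40% band. A patient who meets inclusion criterion 5 has no deviation to code. I07 is also a baseline matter, unrelated to post-endpoint events.

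**Conclusion.** The point holds for the supportive analysis only. The SAP removes a limit that the protocol set, and the effect is that patients with complete, unaffected Week 4 and Week 8 values can leave the PPS because of D01, M01 or possibly E02 events in the open-label weeks. It would be wrong to read this as a threat to the primary result, because the FAS does not use these rules.

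It would also be wrong to claim a known bias towards or away from the null. Under the assumed rates above the ratio lies anywhere from about 0.80 to 0.84 around the planned 0.82, and swapping the arms reverses the direction. Those rates, and the 0.5 log excess, are illustrative assumptions that the documents do not give.

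**What to change.** In SAP 2.2, Section 4 and 5.6, count towards PPS exclusion only deviations dated on or before the Week 8 NT-proBNP sample (or the Week 8 visit, which matches the phase boundary in SAP 2.1.1). This restores the rule in protocol 9.1. The date is always defined where it matters, because O05 already excludes anyone without a Week 8 sample. If the wider rule is kept, the SAP should give the reason.

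As a separate, minor wording check, compare I07 with the original SAP table and align it with inclusion criterion 5: LVEF ≤40%, with all the imaging methods listed there.

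The cost is SAP wording and one date condition in the PPS flag. Deviations are already to be summarized by study phase (SAP 2.3.2), so no new data are needed.
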